2.4 The secondary endpoints

- 1) progressive lung function impairment between 3 and 12 months, defined as $\geq 10\%$ relative decline in FVC, or $\geq 10\%$ relative decline in DLco, or increasing radiological extent of PC-ILD using image analysis [20].
- 2) Resolution of ILD, as defined by $\geq 10\%$ relative improvement in FVC, DLco, or reduction of radiological extent.

- 3) Persistence of ILD in those not meeting definition of progression or resolution
- 4) Presence of interstitial lung abnormalities (ILA) on radiological images that do not meet definition of ILD.
- 5) A comprehensive series of clinical, molecular, MRI and biochemical parameters will be assessed as biomarkers.

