3.1 Study procedures objectives and outcomes

	Objectives	Outcome Measures	Timepoint(s)
Primary	1) Examine and compare the prevalence of ILD in patients with varying severity of COVID-19. (Non-hospitalised will be compared with hospitalised patients and COVID severity defined as varying levels of respiratory support)	MDT diagnosis of ILD at 12 months (+/- 3 months) after acute infection	12 months (+/- 3 months) post SARS-CoV-2 NB: Need 2 time points, 6 months apart, between 3 and 15 months post-acute SARS-CoV-2
Secondary	Determine progressive lung function impairment between 3 and 12 months	Lung function decline: ≥10% relative decline in FVC or DLco OR Imaging deterioration: increasing radiological extent of PC-ILD using image analysis or MDT discussion	Need 2 time points, 6 months apart, between 3 and 15 months post-acute SARS-CoV-2
	Resolution of ILD	Any of the following: ≥10% relative improvement in FVC, DLco, or reduction of radiological extent.	12 months (+/- 3 months) post SARS-CoV-2 Need 2 time points, 6 months apart, between 3 and 15 months post-acute SARS-CoV-2
	Persistence of ILD in those not meeting definition of progression or resolution		12 months (+/- 3 months) post SARS-CoV-2 2 time points, 6 months apart, between 3 and 15 months post-acute SARS-CoV-2
	Persistence of ILAs		12 months (+/- 3 months) post SARS-CoV-2

			Need 2 time points, 6 months apart, between 3 and 15 months post-acute SARS-CoV-2
	In hospitalised patients only: Assess the relationship between initial severity of acute infection and ILD	Markers of severity of acute infection (e.g. CRP)	12 months (+/- 3 months) post SARS-CoV-2 Need 2 time points, 6 months apart, between 3 and 15 months post-acute SARS-CoV-2
	In hospitalised patients only Assess the impact of specific medical therapy used in the acute setting and ILD e.g. antivirals, immunomodulation	Medical therapy used for acute infection	12 months (+/- 3 months) post SARS-CoV-2 Need 2 time points, 6 months apart, between 3 and 15 months post-acute SARS-CoV-2
	Evaluate breathlessness, fatigue and cognition	Medical research council dyspnoea scale Dyspnoea 12 FACIT-F Montreal Cognition Assessment (MOCA)	3 month, 6 months (+/- 6 weeks) and 12 months (+/- 3 months) post SARS-CoV-2 infection
	Evaluate the quality of life of patients with COVID-19	Short Form-36 (SF-36) EQ5D-5L	3 month, 6 months (+/- 6 weeks) and 12 months (+/- 3 months) post SARS-CoV-2 infection

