3.2.1 Baseline and follow up assessments

Initial patient approach

Eligibility assessment by clinical team

Study information and invitation letter provided to eligible patients

Visit 1 (~3 months) (Post COVID-19 infection patients)

1. Review of eligibility with participant
2. Obtain written informed consent
3. History and anthropometric measurements, e.g. height, weight, body mass index (BMI)
4. Blood sample (6-10 ml) collection
5. Pulmonary function test (20 minutes)
6. *Optional* 6-minute walk test (6MWT) (10 minutes)
7. Quality of Life questionnaire (SF-36) (10 minutes)
8. Clinical Frailty Scale (CFS) (5 minutes)
9. Personal health questionnaire (PHQ) (10 minutes)
10. Montreal Cognitive Assessment MOCA (10 minutes)
11. Dyspnea 12 score (10 minutes)
12. EQ5D-5L (10 minutes)
13. FACIT-F questionnaire (10 minutes)

Optional Visit 2 (~6 months) (Post COVID-19 infection patients and matched controls)

All visit 1 assessments will be repeated.

Visit 3 (~12 months) (Post COVID-19 infection patients)

All visit 1 assessments will be repeated.

Visits will be scheduled to take place over 1 day.

Visit 2 is optional,

Visits 1 and 3 are obligatory.

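### The progression and resolution rules can both be met by one participant, and radiological extent has no stated minimum for an increase and an unclear one for a reduction

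*Combined protocol and SAP*

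**What the plan says.** Section 2.4 lists progression, resolution and persistence as secondary endpoints 1 to 3, and the table in 3.1 repeats them.

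- **Progression** is a relative fall of at least 10% in FVC, or the same in DLco, "or increasing radiological extent of PC-ILD using image analysis [20"]. The table in 3.1 widens the imaging arm to "increasing radiological extent of PC-ILD using image analysis or MDT discussion". Neither place gives a minimum change in extent.
- **Resolution**, in the table, is "Any of the following: ≥10% relative improvement in FVC, DLco, or reduction of radiological extent". Section 2.4 has the same three components.
- **Persistence** is "Persistence of ILD in those not meeting definition of progression or resolution".
- **Timing.** Section 3.1 asks for "2 time points, 6 months apart, between 3 and 15 months post-acute SARS-CoV-2".

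Neither section gives an order of precedence, a mixed class, or a requirement that components agree. Section 7.0 groups some biomarker analyses by progression, resolution or persistence, but ties those words to radiological patterns and does not refer back to 2.4.

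**The concern.** Describing the natural history of PC-ILD is a secondary objective (section 2.2), and these three classes are one of the ways the plan does it. Two rules that each need only one of three measures will collide whenever the measures disagree. A participant then enters two opposite classes, and class percentages can add to more than 100. Two analysts following the text faithfully could report different counts from the same data, and the choice between them could be made after the results are seen.

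The second problem is the unequal bar. A 10% margin protects FVC and DLco from ordinary test-to-test variation. Extent has no stated margin for an increase, so a trivial rise carries the same weight as a 10% fall in FVC. Whether a reduction has a margin depends on how one sentence is parsed.

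**Working it through.** The plan gives no figure on this point, so there is none to reproduce.

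**Step 1. Count the patterns (no assumptions).** Score each of FVC, DLco and extent as worse, no qualifying change, or better: 3³ = 27 patterns. Patterns with no measure worse: 2³ = 8, so progression is met in 27 − 8 = 19. By symmetry resolution is met in 19. Neither is met in 1. Both are met in 19 + 19 − 27 + 1 = **12**.

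**Step 2. The two readings of the reduction rule.**
- *Reading A:* the 10% does not govern extent, so any reduction is resolution. Once measured extent differs at all, 2 × 9 = 18 patterns remain: 4 progression only, 4 resolution only, 10 both, 0 neither. With paired CT, persistence needs exactly zero measured change in extent.
- *Reading B:* the 10% governs a reduction. Small reductions stay persistent, but any increase is still progression. The 12 overlapping patterns remain.

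**Step 3. Illustration with no true change.** The documents give no SDs, correlations or baseline extents, so all of these are assumed: normal, independent errors; paired SD of relative change 5% for FVC and 8% for DLco; starting extent 15 to 30%; paired SD of extent 2 to 4 points; extent on a continuous scale.

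- q_F = P(Z > 10/5) = 0.0228; q_D = P(Z > 10/8) = 0.1056
- P(progression) = 1 − (1 − 0.0228)(1 − 0.1056)(0.5) = **0.563** on either reading. The 0.5 comes from symmetric error in extent, whatever its SD.
- Reading A: P(resolution) = 0.563 and P(neither) = 0, so P(both) = 0.563 + 0.563 − 1 = 0.126.
- Reading B: q_R = P(Z > 0.1 × baseline / SD), from P(Z > 3/2) = 0.067 to P(Z > 1.5/4) = 0.354.
  - P(resolution) = 1 − (0.9772)(0.8944)(1 − q_R) = 0.184 to 0.435
  - P(neither) = (1 − 2q_F)(1 − 2q_D)(0.5 − q_R) = 0.753 × (0.433 to 0.146) = 0.326 to 0.110
  - P(both) = 0.563 + P(resolution) − 1 + P(neither) = 0.073 to 0.108

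**Step 4. Sensitivity (simulation; SD pairs 4/6, 5/8 and 6/10%; equal correlation 0 to 0.9 in the same clinical direction; still no true change).**

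| How extent is read | Progression | Both | Neither |
|---|---|---|---|
| Continuous, reading A | 50–60% | 0–20% | 0% |
| Continuous, reading B | 50–60% | 0–17% | 9–42% |
| 5-point steps, either reading | 17–42% | 0–12% | 27–66% |
| No repeat CT, lung function only | 5–20% | 0–1.5% | 62–90% |

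On reading A, overlap is 5–20% at correlation 0, about 1% at most at 0.8, and 0.1% at most at 0.9.

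**Step 5. Does a threshold alone cure it?** Requiring a change in extent beyond 1.96 times its own paired SD, in both directions, gives neither 59–89% and both 0–2.4%. Persistence is restored, but overlap is not removed.

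**The case against.** The strongest reply is that 2.4 lists separate endpoints and never says they form a partition; two binary endpoints may overlap without error. That is fair for the first two taken alone. It does not help persistence, which is built as the residual of both, or a reader told that one participant's ILD has both progressed and resolved.

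Second, the plan does not say that extent is quantitative. Section 2.4 says only image analysis, with a reference whose content cannot be seen, and 3.1 also allows MDT discussion, which need not count trivial change. This stands: the figure of about one half is conditional on a continuous scale.

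Third, a reader might infer that participants with one CT will be misclassified, since 3.2.1 schedules "Pulmonary function test (20 minutes") at the obligatory visits but lists no CT, and Appendix 1 (2.2.4) allows CT at a single time point. The documents do not support that as a firm finding. Section 3.1 requires two time points, and the ordinary reading is that change in a measure needs that measure twice. What remains is that the handling is not spelled out.

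Fourth, calling a 10% gain resolution is explicitly defined, so it is mainly a labelling matter, although such a participant could still have ILD on MDT diagnosis at 12 months.

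**Conclusion.** The point holds on the wording. As written, progression and resolution are not mutually exclusive, an increase in extent has no stated minimum, and the threshold for a reduction is ambiguous. These conclusions and the 12-of-27 count rest on the text alone.

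The size is conditional. With continuous scoring, symmetric error and paired CT, about half of unchanged participants would be labelled progressing. On reading A almost none of those with paired CT could be persistent; on reading B noise favours progression over resolution (56% against 18–44% in the closed-form case). Every percentage uses assumed inputs. Coarse reading lowers them, and strong correlation takes overlap close to zero.

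Three stronger inferences are not supported:
- That 12 of 27, or 44%, of participants would be in both classes. The patterns are not equally likely.
- That the main result is compromised. The primary outcome in 3.1 is "MDT diagnosis of ILD at 12 months (+/- 3 months) after acute infection", which does not use these rules.
- That the biomarker models in 7.0 are contaminated. They are affected only if their groups use this composite; groups based on extent alone could not overlap.

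This should be fixed before the secondary endpoints are analysed.

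**What to change.** 1. In 2.4 and 3.1, name one method for measuring extent and apply one pre-stated minimum change, above that method's measurement error, to increase and reduction alike. Say whether it is relative or absolute.
2. Make the three classes mutually exclusive, either by a pre-stated order or by a separate discordant class. Item 1 does not do this by itself.
3. In 7.0, state whether the biomarker groups use this composite or radiological extent alone.

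Two smaller wording points: call the 10% gain improvement, and report resolution from the early and late MDT diagnoses that 7.0 already plans; and report participants without paired CT separately.

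Cost: items 2 and 3 and the wording points need no new data. Item 1 needs a repeatability figure for the image-analysis method, which the documents do not contain. Fewer participants will be labelled progressed or resolved.

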3.3 Monitoring of clinical events and re-analysis of previous scans (clinically indicated)

Clinical outcome data and images from clinical scans for all COVID-19 patients will also be collected from around the time of infection and hospitalisation and follow up. Laboratory analyses and chest imaging results undertaken for clinical reasons will also be collected. Access to participant medical records and any relevant hospital data that is recorded as part of routine standard of care; i.e., CT-Scans, blood results and disease progression data etc. will be obtained with patient consent from hospital electronic patient records and NHS digital

3.4 Sample Handling Tier 2

Blood samples for the analysis of serum inflammatory markers, serum biomarkers of endothelial and epithelial injury and coagulation studies, viral serology, viral PCR, and whole genome sequencing, ribonucleic acid sequencing and flow cytometry in blood will be collected. Analysis of venous blood samples will be performed in local NHS laboratories. If the Participant consents approximately 10 ml of blood will be stored in the Division of Cardiovascular Medicine for further analysis as part of collaborations with other groups. Samples will not be collected from participants who are also participating in PHOSP-COVID

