6.4 Serious AEs

An SAE form should be completed and emailed to the Chief Investigator within 24 hours. However, relapse and death due to COVID -19, and hospitalisations for elective treatment of a pre-existing condition do not need reporting as SAEs.

All SAEs should be reported to the London Riverside REC where in the opinion of the Chief Investigator, the event was:

- 'related', ie resulted from the administration of any of the research procedures; and
- 'unexpected', ie an event that is not listed in the protocol as an expected occurrence

Reports of related and unexpected SAEs should be submitted within 15 days of the Chief Investigator becoming aware of the event, using the NRES SAE form for non-IMP studies. The Chief Investigator must also notify the Sponsor of all related and unexpected SAEs.

Local investigators should report any SAEs as required by their Local Research Ethics Committee, Sponsor and/or Research & Development Office.

Contact details for reporting [contact]**CI email (and contact details below)****Fax: N/A, attention [name]****Please send SAE forms to: [contact]****[contact] (Mon to Fri 09.00 – 17.00)****7.0 STATISTICS AND DATA ANALYSIS**

The prevalence of MDT-confirmed PC-ILD at both early (up to 6 months) and again at late (10-15 month) time-points and will be assessed within the total study population. The prevalence of broader radiological abnormalities and phenotypic patterns will also be assessed in a descriptive analysis, together with demographics, haematological and biochemical profiles, physiological performance, and patient-reported outcome measures. Analyses will be performed overall and stratified according to hospitalised and non-hospitalised, as well as severity of infection in hospitalised patients defined above.

Baseline and longitudinal changes in biomarkers reflecting PC-ILD evolution, including circulating factors and cell-types from detailed serological and cellular analysis, will be assessed in multilevel models for repeated measures to test associations according to the presence or absence of PC-ILD at late time points (10-15 months), and according to progression, resolution, or persistence of radiological patterns over follow up time points.

Analyses will be performed using standard epidemiological and statistical genetics methodology. This will include cross-sectional and longitudinal studies, and analyses of disease prevalence and incidence.

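### Participants with early PC-ILD who die of respiratory disease or become too ill to test, with no qualifying later measurement, have no place in the progression, resolution and persistence outcomes

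*Combined protocol and SAP*

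**What the plan says.** Section 2.4, item 1, sets the endpoint as "progressive lung function impairment between 3 and 12 months, defined as" a relative fall of at least 10% in FVC or in DLco, "or increasing radiological extent of PC-ILD using image analysis". Section 3.1 gives the imaging route as "increasing radiological extent of PC-ILD using image analysis or MDT discussion", which adds multidisciplinary review but keeps it under imaging deterioration. Resolution (2.4, item 2) needs an improvement of the same size in lung function or a "reduction of radiological extent". Persistence (2.4, item 3) is the remainder: "Persistence of ILD in those not meeting definition of progression or resolution".

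In 3.1 the progression, resolution and persistence rows each ask for two time points 6 months apart, both between months 3 and 15. Section 2.4 has no such interval.

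Section 7 compares biomarkers between participants whose radiological patterns progress, resolve or persist. It also says that analyses will be run overall and by hospitalisation and severity of infection.

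On sources, section 3.3 says that routine-care data, including "disease progression data etc. will be obtained with patient consent from hospital electronic patient records and NHS digital".

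**The concern.** Every route to progression or resolution needs a later measurement. A participant with early PC-ILD who dies of respiratory failure at month 8, or who cannot perform lung function tests at month 12 and has no later CT, supplies none. These are among the worst courses the disease can take, and the three-way classification has no place for them.

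The second objective in section 2.2 is the natural history of PC-ILD, and the third is to find prognostic biomarkers. If the worst outcomes are left out, progression is under-reported, and markers that predict respiratory death are tested in a cohort from which those deaths have been removed. If such losses are more common after severe acute infection, the severity-stratified results are attenuated as well.

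**Working it through.** The plan states no progression rate, death rate, sample-size basis or missing-data rule for this endpoint, so there is no figure of its own to reproduce. The check has four parts.

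**1. Is there a rule anywhere?** The endpoints (2.4, 3.1), withdrawal criteria (4.4), follow-up (5.1), adverse events (6.1 to 6.4) and statistics (7.0) were read for one. Section 4.4 foresees withdrawal because a participant cannot comply with procedures, but attaches no outcome to it. None of these sections classifies death or inability to be tested, and none names a competing event. The restriction to survivors appears only in the primary objective (2.1) and is not carried into these endpoints.

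**2. When can the second measurement fall?** Under 3.1 the earliest is 3 + 6 = month 9. The optional 6-month visit does not help. Six weeks is 42/30.44 = 1.38 months, so at its latest that visit is at month 7.38, which is 4.38 months after a month-3 baseline. Even if visit 1 were 6 weeks early (month 1.62, outside the 3-to-15-month window), the gap is 5.76 months. Under 3.1, therefore, someone lost before month 9 cannot be a progressor, even with a worse interim scan. Under 2.4 alone, that scan could count.

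**3. Where do these participants go?**
- Under 3.1, whose persistence row carries the two-time-point requirement, they cannot be classified and drop out.
- Under the bare wording of 2.4, item 3, they meet neither other definition and so count as persistent.

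The documents do not say which section governs.

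**4. How large could the effect be?** Take 100 participants with early ILD. Let *m* be the number with measured progression, and *d* the number with respiratory death or respiratory untestability and no qualifying later measurement. Both are assumptions. Everyone else is taken to be measured.

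- Combined outcome: (*m* + *d*)/100
- Dropped: *m*/(100 − *d*)
- Relative shortfall: 1 − dropped/combined

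With *m* = 20:

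| *d* | Combined | Dropped | Relative shortfall |
|---|---|---|---|
| 1 | 21/100 = 21.0% | 20/99 = 20.2% | 3.8% |
| 5 | 25/100 = 25.0% | 20/95 = 21.1% | 15.8% |
| 10 | 30/100 = 30.0% | 20/90 = 22.2% | 25.9% |

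Over *m* = 10 to 30 and *d* = 1 to 10, the shortfall from dropping runs from 2.2% (*m* = 30, *d* = 1) to 44.4% (*m* = 10, *d* = 10).

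**Severity contrast (illustration).** Assume 20% progression among those measured in both groups, with 10% lost in this way after severe infection and 1% after mild.

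- Combined: 0.20 × 0.90 + 0.10 = 28.0% against 0.20 × 0.99 + 0.01 = 20.8%, ratio 1.35.
- Dropped: 20% against 20%, ratio 1.00.

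With 5% against 1% lost, the combined ratio is 24.0/20.8 = 1.15, and dropping again gives 1.00.

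**The case against.** The strongest reply is that the gap is narrow. Clinical scans are collected for all participants (3.3, 5.1), and the imaging appendix (2.2.4) collects all follow-up images. Someone too breathless for spirometry may still have a later CT, and 3.1 allows multidisciplinary review. This stands: a reader might infer that anyone who dies or becomes untestable is never a progressor, and the documents do not support that. The point covers only those with no qualifying later measurement or image.

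A reader might also infer that the plan records the dead as having stable disease, and take that as the main harm. The persistence row in 3.1 carries the two-time-point requirement, and section 7 groups by radiological patterns over follow-up. Exclusion is therefore the likelier result; the persistent label follows only from 2.4 read alone.

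Section 6.4 says that "relapse and death due to COVID -19, and hospitalisations for elective treatment of a pre-existing condition do not need reporting as SAEs". It is tempting to conclude that these deaths would go uncaptured. That does not follow: a safety-reporting exemption does not decide endpoint capture, respiratory death from PC-ILD is not clearly within it, and 3.3 gives access to records.

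Two further objections stand in part. Section 4.3 excludes life-limiting illness within 12 months, which should lower deaths but cannot prevent deterioration after entry. And endpoint 1 is named as lung function impairment, so folding death into it changes its meaning. A separate category or a competing-event analysis is also defensible. That is a reason to choose a rule in advance and to report both versions.

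**Conclusion.** The concern holds in this limited form. Sections 2.4 and 3.1 have no outcome for participants with early PC-ILD who die of respiratory disease or become too ill to test with no qualifying later measurement, and the two sections send them to different places. Both routes understate progression relative to an outcome that counts these events.

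The size is not known. Under the assumption of 20 measured progressors per 100, the gap is 21.0% against 20.2% with 1 such case, which is negligible, and 30.0% against 22.2% with 10. The loss of the severity contrast depends on a further assumption, that these cases concentrate in severe disease; the documents give no figure for it.

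These are secondary endpoints of an observational cohort, and the primary endpoint is outside this point. The change should be made before analysis, so that the rule is not chosen with the data in view.

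**What to change.** Amend 2.4, 3.1 and section 7 together:

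- **Persistence.** Limit it to participants alive and measured at both time points, so that 2.4 agrees with 3.1.
- **New category.** Add a named outcome for respiratory death, lung transplantation, or inability to be tested because of respiratory disease, after an early ILD diagnosis and before the late time point. Take it from the hospital-record and NHS Digital access in 3.3. Report deaths from other causes separately.
- **Reporting.** Give progression as measured decline alone and as measured decline combined with the new category, each with all participants with early ILD in the denominator. Use the combined version in the severity and prognostic-biomarker analyses, at least as a prespecified sensitivity analysis.

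The cost is endpoint wording, a field on the case report form for the reason a participant was not tested, and modest record review to classify cause of death. The main downside is some uncertainty in cause-of-death coding, which showing both versions makes visible.
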